## **9.5 Halting Rules**

### **9.5.1 Discontinuation of Study Participation for Individual Subject**

Subjects with neutropenia, thrombocytopenia, or hepatotoxicity while on study medication will be discontinued from study treatment if the criteria outlined in Section 6.3 (Modification or

---

Termination of Study Intervention/Investigational Product for a Participant) or in Section 5.3.3 (Reasons for Withdrawal) are met. Since the primary endpoint requires comparison of baseline and 6 month audiology assessments, dropouts and subjects with audiology assessments that are inadequate for study comparison will be replaced in order to reach the target of sample size.

### **9.5.2 Discontinuation of Study Enrollment, and Study Treatment For All Subjects, Pending Sponsor Review**

Enrollment and study product administration will be halted for Safety Monitoring Committee (SMC) review/recommendation if any of the following is reported:

- Two or more subjects experience a study product-related SAE.
- 10% or more subjects (with a minimum of 3 subjects) experience the same severe (Grade 3 or higher) study product-related unsolicited AE.
- 20% or more subjects (with a minimum of 3 subjects) experience the same severe (Grade 3 or higher) study product-related non-neutropenia safety laboratory AE.
- 30% or more subjects (with a minimum of 3 subjects) experience severe (Grade 3 or higher) study product-related neutropenia safety laboratory AE.
- 10% or more subjects (with a minimum of 3 subjects) permanently discontinue study treatment according to the criteria outlined in Section 6.3.

Additionally, DMID and the Central Unit may interrupt study dosing and/or study entry at any time if medically indicated. To minimize risk, the medical monitor and the SMC will review cumulative safety data. If enrollment is halted based upon the study halting criteria above or the review of the safety data, upon completion of the review and receipt of advice of the SMC, DMID and the Central Unit Administration will determine if study entry or study dosing may continue according to the protocol.

## **9.6 Safety Oversight (SMC)**

Safety oversight will be conducted by an SMC that is an independent group of experts that monitors subject safety and advises DMID. The SMC members will consist of persons independent of the investigators or study team with no financial, scientific, or other conflict of interest with the study, and will be selected by Sponsor (DMID). The SMC will consist of members with appropriate expertise to contribute to the interpretation of the data from this trial. The SMC meetings will include the following: an organizational meeting; scheduled data reviews; ad hoc (for identified safety issues) meetings as needed; and the final meeting at the end of the study when the final clinical study report is available.

---

The initial responsibility of the SMC will be to review and make recommendations regarding the initiation of the study. A simple majority will be considered a SMC quorum for voting and meeting purposes. Members will be able to submit data review comments electronically if they are not able to participate in a data review meeting teleconference. After the initiation of the study and during the course of the study, the SMC will convene at as follows: when 20% of enrolled subjects have available safety data through 4 weeks following the last study product administration, and at least once annually thereafter. A final SMC review meeting will take place 6 to 8 months after clinical database lock to review the cumulative unblinded safety and immunogenicity data for this trial. The data will be provided in a standard summary format. The SMC may be asked to provide recommendations in response to questions posed by DMID.

The SMC will operate under the rules of a DMID-approved charter that will be written at the organizational meeting of the SMC. At this time, each data element that the SMC needs to assess will be clearly defined. Procedures for SMC reviews/meetings will be defined in the charter. The SMC will review applicable data to include, but not limited to, study progress and participant, clinical, and safety data. Reports may include enrollment and demographic information, medical history, concomitant medications, physical assessments, clinical laboratory values, dosing compliance, and solicited and unsolicited AE/SAEs. Additional data may be requested by the SMC, and interim statistical reports may be generated as deemed necessary and appropriate by DMID. The SMC will meet and review these data at the intervals determined by the SMC charter, or ad hoc as needed during this trial. As an outcome of each review/meeting, the SMC will make a recommendation as to the advisability of proceeding with study vaccinations (as applicable), and to continue, modify, or terminate this trial.

Additionally, Statistical and Data Coordinating Center (SDCC) web reports using data entered into AdvantageEDC will be monitored to determine if any of the halting rules described in Section 9.5 (Halting Rules) are met.

### **9.6.1 Independent Safety Monitor (ISM)**

For certain clinical trials, DMID will require an Independent Safety Monitor (ISM) to be assigned for each study site and the requirement for an ISM will be specified in the protocol. An ISM is a physician with relevant expertise whose primary responsibility is to provide to DMID an independent safety assessment in a timely fashion. Participation is for the duration of the DMID study and is a voluntary position that does not receive payment. The ISM must meet the requirements of the NIAID conflict of interest policy.

**For this clinical trial an ISM is not required.** However, at each participating site, **upon DMID Medical Monitor request**, the principal investigator (PI) will identify a physician with

relevant expertise, to act as a Secondary Medical Assessor (SMA). The SMA will examine a subject and/or medical records and provide a medical assessment (or second medical opinion) to the DMID of the safety event in question. The PI will send to the DMID MM, a summary of the event and include the PI and SMA assessments.

Note: In the case that DMID has requested this type of evaluation multiple times, DMID may request the site(s) identify an ISM to assist DMID with safety oversight.

---

## 10 CLINICAL MONITORING

### 10.1 Site Monitoring Plan

Site Monitoring will be conducted to ensure that human subject protection, study procedures, laboratory procedures, study intervention administration, and data collection processes are of high quality and meet sponsor, ICH/GCP, and regulatory guidelines, and that the study is conducted in accordance with the protocol and study manuals. DMID, the sponsor of this study, or its designee will conduct site monitoring visits as detailed in the monitoring plan.

Site visits will be made at standard intervals in accordance with the monitoring plan. More frequent visits may be made if needed. Monitoring visits will include, but are not limited to, review of informed consents, source documentation, hospital records, clinical and office charts, laboratory notes, memoranda, evaluation checklists, pharmacy dispensing records, recorded data from automated instruments, copies or transcriptions certified after verification as being accurate and complete, microfiches, photographic negatives, microfilm or magnetic media, x-rays, and subject files and records kept at the pharmacy, at the laboratories, and medico-technical departments involved in the clinical trial. Data collection forms used as source documents will be derived from the eCRFs and be provided by the SDCC. Study monitors will meet with investigators to discuss any problems and actions to be taken and document visit findings and discussions.

---

## 11 STATISTICAL CONSIDERATIONS

### 11.1 Study Hypotheses

Given the benefit demonstrated from longer-term antiviral treatment of babies with symptomatic congenital CMV disease, and recognizing the fact that most of the disease burden of CMV-associated hearing loss is in the asymptotically infected population, we hypothesize that infants with asymptomatic congenital CMV infection who are treated with valganciclovir will have protection against hearing deterioration.

### 11.2 Sample Size Considerations

This is a Phase II, multi-center, single-stage, single-arm (open label) evaluation of 4 months of valganciclovir treatment for infants with virologically-confirmed congenital CMV infection who are asymptomatic at birth. The study sample size is 176 male and female infants under 1 month of age with asymptomatic congenital CMV infection without baseline sensorineural hearing loss (SNHL) who are evaluable for the primary endpoint. The goal of the study is to investigate the possible efficacy of valganciclovir therapy in asymptomatic infants congenitally infected with CMV for the prevention of SNHL. All infants enrolled will be given valganciclovir per the protocol. Since the hearing assessments will be based on specific measurements from brainstem auditory evoked response (BSER) evaluation of hearing, which yields objective data, there will not be bias in the measurement of hearing outcomes due to the open label design. A 95% estimate of the upper bound for the true proportion of asymptomatic infants who will develop SNHL by the time they are 6 months of age will be calculated using the exact Clopper-Pearson method. Table 3, below, displays the different sample size scenarios and the estimated upper bound if (1) none, (2) exactly 1, and (3) exactly 2 out of the total sample size develop SNHL. Given our sample size of 176 subjects, the 95% upper confidence bound for the true proportion who will develop SNHL within 6 months of birth is 1.69% and 2.67% if none or exactly 1, respectively, develops SNHL. If these scenarios are observed, they will provide preliminary evidence that valganciclovir treatment of infants with asymptomatic congenital CMV infection may decrease the rate of SNHL based on the landmark study by Dahle et al. that estimates 3.18% of asymptomatic CMV infected infants develop SNHL by 6 months of age. Knowledge of these confidence bounds will allow us to estimate whether antiviral therapy in this population is likely to be of benefit. If the 95% upper confidence bound is lower than the 3.18% estimate from Dahle et al., our data would suggest the possibility of treatment benefit. Upon completion of the audiology analyses from the CHIMES study (which screened 100,000 neonates for asymptomatic congenital CMV infection at seven study sites in the United States from March 2007 through November 2009 and then followed them for audiological outcomes over the first several years of life), we will compare our 95% upper confidence bound with the contemporaneous CHIMES estimates as well.

Table 3. Sample Size and Upper Bound of Estimates of SNHL

Sample Size	95% Upper Bound Assuming No Subjects Develop SNHL	95% Upper Bound Assuming One Subject Develops SNHL	95% Upper Bound Assuming Two Subjects Develop SNHL
80	3.68%	5.79%	7.66%
100	2.95%	4.66%	6.16%
150	1.98%	3.12%	4.14%
176	1.69%	2.67%	3.50%

Approximately 229 subjects with asymptomatic congenital CMV infection without SNHL will be identified and offered enrollment in order to meet the sample size requirements of 176 evaluable subjects. A recent NIDCD study designed to develop screening methodologies for detection of congenital CMV infection (the CHIMES Study, PI: [name], who is a co-investigator in this trial) determined that 0.5% of neonates born in the United States have congenital CMV infection, although higher rates of 0.6% to 1.0% were seen in southern states. Additionally, CHIMES data also suggest that 4.9% of neonates with asymptomatic congenital CMV infection will have baseline SNHL and 95.1% will have normal hearing at birth ([name], personal communication). Therefore, to detect 229 neonates with asymptomatic congenital CMV infection without baseline SNHL to offer enrollment in this trial, an anticipated 48,250 babies will be screened for congenital CMV infection by buccal saliva swab PCR, the high sensitivity of which (97.4%) was recently reported by the CHIMES investigators. A *screening* informed consent form will be utilized for permission to conduct the screening test. Of these 48,250 infants, we anticipate that 241 (0.5%) will have asymptomatic congenital CMV infection. This is a conservative estimate, since we have selected study sites that are in regions of the country where congenital CMV incidence rates are in the 0.6% to 1.0% range. Babies screening positive for congenital CMV infection will have sensorineural hearing testing performed, as is standard of care for babies identified as being congenitally infected with CMV. A second saliva sample and a urine sample will be collected by study personnel (which will be covered by the *screening* informed consent) for confirmatory PCR testing. The likelihood of a false-positive screening test is < 0.03%, but performing a confirmatory test ensures that only those babies truly infected with CMV will be exposed to valganciclovir. We estimate that 12 patients (4.9% of 241) will have baseline SNHL, and that 229 patients (95.1% of 241) will have normal hearing. These approximately 229 asymptotically infected neonates without sensorineural hearing loss will be assessed for all inclusion criteria, and offered enrollment on the treatment portion of the trial if they meet all inclusion criteria and no exclusion criteria. The approximately 12 patients identified as being asymptotically congenitally infected with CMV and with SNHL very likely will be treated clinically with 6 months of oral valganciclovir. If

### **11.3 Planned Interim Analyses (if applicable)**

There will be no interim analyses for efficacy for this study. The demographics of the screened population may be assessed and presented prior to completion of the study.

## **11.4 Final Analysis Plan**

### **11.4.1 Analysis Populations**

#### **11.4.1.1 Intent to Treat Population**

Any child who receives at least one dose of study medication will be included in an intention to treat (ITT) analysis of safety.

---

#### **11.4.1.2 Per Protocol Population**

Children who complete the full four months of study medication will be included in a per protocol (PP) analysis of efficacy.

#### **11.4.1.3 Safety Population**

The Safety Population will consist of all subjects who have received at least one dose of study product and for whom any data on safety are available.

#### **11.4.1.4 Screened Population**

The Screened Population will consist of all patients who signed the *screening* informed consent and for whom the saliva PCR for CMV DNA is available.

### **11.4.2 Baseline Characteristics**

Baseline characteristics will be summarized. For both continuous and categorical variables, appropriate summary statistics will be applied. For continuous variables, descriptive statistics will include the number of non-missing values, mean, standard deviation, median, minimum, and maximum. For categorical variables, descriptive statistics will include counts and percentages per category.

### **11.4.3 Safety Analysis Plan**

Safety evaluations will be based on the incidence, severity, and type of AEs. Safety variables will be tabulated and presented for all subjects in the safety population. All tests will use a 5% significance level, i.e.,  $p$ -values  $< 0.05$  will be considered significant, and for estimation a 95% confidence level will be used.

### **11.4.4 Efficacy Analysis Plan**

Primary analysis:

The primary analysis is estimating the proportion of subjects with asymptomatic congenital CMV infection who, following treatment with 4 months of oral valganciclovir, develop SNHL by 6 months of life in at least one ear. Due to the small expected number of subjects who will develop SNHL by 6 months, the Clopper-Pearson method will be used to calculate an exact 95% upper confidence bound for the primary outcome.

Secondary analyses:

---

For the proportion of subjects who develop SNHL at 4, 12, and 18 months post baseline, we will also use the Clopper-Pearson method to obtain an estimate of the 95% upper confidence bounds separately for each period. In each of these hearing outcomes, we will provide a breakdown on the degree of worsening (mild, moderate, severe). This method will also be used to define safety and tolerability of valganciclovir by estimating the incidence of adverse events of interest. If there is enough information in the data collected, we will use a large-sample method for estimating the 95% confidence interval of interest over the more conservative Clopper-Pearson method.

Analysis of actual viral load will be done using log base 10 transformation for both whole blood and plasma CMV viral loads. Undetectable viral load value will be replaced by a value of 10. To investigate the change over time, we will model the log base 10 viral load using mixed model to accommodate repeated measures. The covariance structure (selected among unstructured, exchangeable, autoregressive, exponential, and toeplitz) that best describes the correlation among the repeated measures over time will be selected using the AIC model selection index. Note that there will be 13 time points for which viral load will be measured. Hence, if time will be represented as discrete variables in the model, this will require spending 12 degrees of freedom in the model, which we believe is unnecessary. In our modeling we will represent time as a continuous variable and will consider fitting linear, quadratic, and cubic to approximate non-linear trends. The simplest model with a good fit based on the test of the coefficients, as well as the profile curves, will be selected. Modeling will be done separately for whole blood and plasma viral loads.

The same method of modeling will be employed to compare the whole blood and plasma CMV viral loads. However, the outcome will be the difference between the whole blood and plasma CMV viral load values for each subject at each time point. If the differences over time are found to be modeled by a linear function and there is no evidence to show that the slope of this line is significantly different from zero, then there is no evidence to conclude a difference between the average viral loads based on whole blood and plasma. Otherwise, there is a difference and this difference will be examined and discussed in more details based on the results of the fitted model.

We will investigate the how viral load is related to hearing outcomes using generalized linear model for binary outcome at each time point relative to baseline hearing.

All tests will use a 5% significance level, i.e., p-values<0.05 will be considered significant.

Ganciclovir resistance will be assessed by molecular methodologies (e.g., deep sequencing, Sanger sequencing, PCR). Blood, urine, and saliva specimens will be obtained serially.

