Of the 109 participants, 21 (19%) had grade 3 or 4 neutropenia during the first 6 weeks of open label valganciclovir therapy. From week 6 through month 6, a total of 10 of the 47 participants (21%) who received the active drug had grade 3 or 4 neutropenia, as compared with 13 of 49 (27%) who received placebo ( $P = 0.64$ ). A total of 3 participants had the drug temporarily suspended because of an absolute neutrophil count of less than 500 per cubic millimeter. All treatment interruptions occurred within the first 6 weeks of the study, and treatment was resumed after resolution of the neutropenia. The alanine aminotransferase and aspartate aminotransferase levels increased slightly at months 4 and 5 in the group of participants who received the active drug, although the differences between this group and the group that received placebo were not statistically significant ( $P > 0.59$  for both aminotransferase comparisons) or clinically significant (all mean values,  $< 90$  U per liter). No deaths occurred. There were no significant differences in the rate of adverse events between the two study groups.

Approximately 10% of asymptomatic children will develop SNHL. This is much higher than the 0.1%–0.4% incidence of hearing loss within the general population. Of CMV-associated SNHL by 4 years of age, almost 75% occurs in children who were asymptotically infected at birth. Many prospective studies of children with asymptomatic congenital CMV infection showed that approximately half of children with asymptomatic infection who develop hearing loss will have bilateral deficits, which can vary from mild high-frequency loss to profound impairment. Moreover, hearing loss in these children is often progressive and/or delayed onset requiring ongoing audiologic evaluation.

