considering similar legislation in their 2015 legislative sessions. This type of “targeted screening” for congenital CMV infection will not identify the overwhelming majority of at-risk neonates, since only 25% of babies with asymptomatic congenital CMV who ultimately develop CMV-associated SNHL have hearing loss present in the first month of life (with the remaining 75% developing hearing loss in later months or the first few years of life). However, targeted screening portends universal screening for congenital CMV infection, as has recently been recommended by a Consensus Conference of leading world experts who gathered before the 5th International Congenital CMV Conference in Brisbane, Australia, on April 19, 2015. A similar staged implementation was seen in the 1990s with hearing screening, whereby testing newborns for hearing abnormalities began in a targeted fashion and only later expanded to universal hearing screening for all babies born in the United States. Once asymptomatic babies are identified through targeted or universal screening programs, there will be tremendous pressure on the managing physician to “do something,” which inevitably will mean treating with oral valganciclovir. Therefore, the window of time to assess the benefit, if any, versus the risk in the asymptotically infected congenital CMV population is narrow. Failure to establish the estimates of clinical effectiveness and to define the risks from treatment now could lead to widespread treatment outside of the confines of a clinical trial, thereby putting babies treated in such a manner at risk of harm with no opportunity to assess for evidence of benefit.

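### Does the option to replace the exact bound with an unnamed large-sample interval for the secondary SNHL and adverse-event rates need to be pinned down?

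*Combined protocol and SAP*

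**What the plan says.** Section 11.4.4 treats the primary and secondary rates separately. For the primary rate it is unconditional: "the Clopper-Pearson method will be used to calculate an exact 95% upper confidence bound for the primary outcome". Under the secondary analyses it uses the same method for SNHL at 4, 12 and 18 months, to "obtain an estimate of the 95% upper confidence bounds separately for each period", and carries it over to safety: "This method will also be used to define safety and tolerability of valganciclovir by estimating the incidence of adverse events of interest".

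The switch comes next. Its condition is "If there is enough information in the data collected" and its consequence is "we will use a large-sample method for estimating the 95% confidence interval of interest over the more conservative Clopper-Pearson method". Section 11.4.3 adds only that "for estimation a 95% confidence level will be used". Nothing else in section 11 gives an event count, a method name or a statement of sidedness for these rates.

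**The concern.** Three things are open: when the switch applies, what replaces the exact bound, and whether the replacement is one- or two-sided. The wording also moves from upper bounds to a confidence interval. The condition refers to the collected data, and the trial is open label with a single arm, so the choice could be made knowing which limit looks better.

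The counts could be large enough for this to arise. Section 2.1 says "Approximately 10% of asymptomatic children will develop SNHL", and section 2.2 puts a quarter of that hearing loss in the first month, "with the remaining 75% developing hearing loss in later months or the first few years of life". Taken together, that is 10% × 75% = 7.5% of asymptomatic children with delayed loss. Section 2.1 also reports grade 3 or 4 neutropenia in 19% during the first six weeks of valganciclovir in an earlier trial. If the replacement were a plain Wald limit, the upper bounds would be too low, and a bound could even fall as events are added across the switch point. Readers of a single-arm study rely on such limits.

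**Working it through.** **Inputs.** n = 176 evaluable infants (section 11.2); n = 218 expected to enrol (section 11.2), as an illustrative safety denominator; the 7.5% and 19% rates above. Assumed, because the documents do not give them: Wald or Wilson as the large-sample method, a switch at 5 or 10 events, and 176 as the denominator at the later visits.

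**Formulas for x events in n, with p = x/n and z = 1.645 (one-sided 95%).**
- Exact: the 0.95 quantile of Beta(x + 1, n − x).
- Wald: p + z√(p(1 − p)/n).
- Wilson: [p + z²/(2n) + z√(p(1 − p)/n + z²/(4n²))] / (1 + z²/n).

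**The plan's own figures.** At n = 176 the exact formula gives 1.69% for no events and 2.67% for one, as stated in section 11.2. The 0.975 quantile would give 2.07% and 3.12%, so the plan's bounds are one-sided. Eleven of the twelve cells of Table 3 reproduce. The other (176 infants, two events) computes to 3.53% against a printed 3.50%, which has no bearing here.

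**Ten events in 176.** p = 0.05682 and √(p(1 − p)/n) = 0.01745.
- Wald: 0.05682 + 1.645 × 0.01745 = 0.0855.
- Wilson: (0.05682 + 0.00769 + 1.645 × 0.01807) / 1.01537 = 0.0928.
- Exact: 0.0945.

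**One-sided upper limits**

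| Events / n | Exact | Wilson | Wald |
|---|---|---|---|
| 5 / 176 | 5.88% | 5.72% | 4.90% |
| 10 / 176 | 9.45% | 9.28% | 8.55% |
| 18 / 176 | 14.79% | 14.61% | 13.98% |
| 40 / 218 | 23.21% | 23.04% | 22.66% |

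In these rows Wilson is 0.16 to 0.18 point below exact. Wald is 0.98 point below at 5 events, 0.90 at 10, 0.81 at 18 and 0.55 at 40 of 218. A two-sided Wilson interval has an upper limit of 10.14% at 10 of 176, but that is a different quantity and should not be ranked against one-sided bounds.

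**The falling bound, if Wald is used.** With a switch at 5 events, 4 events give 5.13% (exact) and 5 give 4.90% (Wald). With a switch at 10, 9 events give 8.75% and 10 give 8.55%.

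**One-sided coverage at n = 176, summed over Binomial(n, p)**

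| True rate | Exact | Wilson | Exact, then Wald from 5 | Exact, then Wald from 10 |
|---|---|---|---|---|
| 3.18% | 97.7% | 97.7% | 97.7% | 97.7% |
| 5% | 97.8% | 94.2% | 91.4% | 97.8% |
| 7.5% | 95.7% | 95.7% | 91.7% | 95.7% |
| 10% | 97.0% | 94.4% | 90.5% | 90.5% |
| 19% | 96.1% | 96.1% | 94.0% | 94.0% |

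At 1% and 2% both Wald hybrids stay at 97% or above. At 19% with n = 218 they cover 94.2%.

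**The case for a change.** The best case for a change is that the harm depends on an unstated choice, and that stating the choice is nearly free. At a true rate of 10%, a Wald replacement covers 90.5% under either assumed switch point. The documents form a combined protocol and SAP, and the section does not defer the matter to a later one. Keeping the exact bound throughout would cost less than 0.2 point against Wilson.

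The textual part stands: trigger, method and sidedness are not written down. The numerical part stands only for Wald. Every coverage figure below 94% and every falling bound needs Wald together with a switch point that the plan does not contain. With a switch at 10 events, coverage at 7.5% is 95.7%, so nothing is lost at the SNHL rate that motivated the worry. That rate is itself generous: it spans the first few years, follow-up ends at 18 months, and it is a background rate, whereas section 11.1 hypothesises protection under treatment.

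The low cost does not settle the matter either. The sponsor chose to allow a less conservative interval when counts support it. Requiring exact limits everywhere would replace that choice with another defensible one. Making one-sided upper bounds compulsory for adverse events would also remove lower limits that section 11.4.3 leaves available.

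**Conclusion.** No change is needed. The gap is real but is the kind that an analyst fills sensibly. The condition works as an as-appropriate clause: sparse data stay on the exact method, and a large-sample limit is used only where counts support it. A statistician following it with a standard score interval would report limits within about 0.2 point of exact at the counts examined. Even under Wald the shift is about 0.9 to 1 point at 5 to 10 events of 176, and about half a point at 40 of 218.

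No stated conclusion depends on the choice. The 3.18% comparison belongs to the Month 6 rate, which stays on Clopper-Pearson, and no threshold is set for SNHL at Months 4, 12 or 18 or for any adverse-event incidence analysed under this sentence. These limits are descriptive, and a reader given the counts and denominators can recompute any of them.

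This rests on the analyst not using plain Wald at low counts, and on the report saying which interval was used, as is usual. The switch points and later-visit denominators used above are illustrations, not figures from the plan.

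### Setting undetectable viral loads to 10 can create a false time trend in the whole blood minus plasma difference when the fluids are offset or their detection limits differ

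*Combined protocol and SAP*

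**What the plan says.** The viral load rules are in section 11.4.4 of the combined protocol and SAP.

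- Scale: "Analysis of actual viral load will be done using log base 10 transformation for both whole blood and plasma CMV viral loads".
- Values below detection: "Undetectable viral load value will be replaced by a value of 10". On the log10 scale this is 1.0, in both fluids.
- Comparison of fluids: "The same method of modeling will be employed to compare the whole blood and plasma CMV viral loads", except that "the outcome will be the difference between the whole blood and plasma CMV viral load values for each subject at each time point". The log scale is not restated for the difference; I read it from the carry-over of method.
- Decision: if the difference is adequately described by a straight line and "there is no evidence to show that the slope of this line is significantly different from zero", the plan finds no evidence that the fluids differ. Any other result is read as a difference and explored further.
- Level: "All tests will use a 5% significance level, i.e., p-values<0.05 will be considered significant".

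Section 3.1 lists the comparison of changes in the two fluids as an exploratory objective. Section 8.2.2.1 says only that quantitative PCR is done at the central laboratory and gives no detection limit. Section 11.4.5 deals with missing safety and hearing data, not with values below detection. The documents name no censored-data method and no sensitivity analysis for undetectable values.

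**The concern.** An undetectable result means that the load lies somewhere below the assay limit. Replacing it with a fixed number treats it as measured. When the lower fluid drops out first, it is pinned at 1.0 while the other is still measured. When both drop out, the difference is forced to 0. If the limit is above 10, a value also jumps down from the limit to 10 as it crosses. The recorded difference then changes over time although the true one does not.

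Section 2.1 reports that whole blood load fell on valganciclovir in the earlier trial in symptomatic infants, so a changing share of undetectable values is to be expected. Change over time is both what the objective asks about and what the slope test examines. The trial could therefore report that the fluids respond differently to treatment when they do not.

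**Working it through.** **1. The plan's own figure.** Section 7 schedules viral load on Days 1, 7, 14, 21, 28, 35, 42, 56, 70 and 84 (10 visits) and Months 4, 5 and 6 (3 visits): 10 + 3 = 13, and 13 - 1 = 12 degrees of freedom. This agrees with "Note that there will be 13 time points for which viral load will be measured".

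**2. Inputs.** From the documents: 13 visits, the 5% level (taken as two-sided), substitution of 10, and 176 infants (section 11.2). Assumed, because the documents are silent: starting load, fall on treatment, offset between fluids, detection limits and standard deviations. The true slope of the difference is 0 throughout.

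**3. One infant.** Take a whole blood start of 3.5 log10, a fall of 1.5, plasma always 1.0 lower, and a limit of 300 (2.48 log10) in both fluids.

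| Point | True whole blood, plasma | Recorded | Recorded difference |
|---|---|---|---|
| Start | 3.50, 2.50 | 3.50, 2.50 | 1.00 |
| Half the fall | 2.75, 1.75 | 2.75, 1.00 | 1.75 |
| Full fall | 2.00, 1.00 | 1.00, 1.00 | 0.00 |

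The true difference is 1.00 at every point.

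**4. Expected values.** For a normal log10 load with mean m, SD s and limit c, put z = (c - m)/s. The mean after substitution is 1·Φ(z) + m·(1 - Φ(z)) + s·φ(z). With assumed SDs of 0.8 between infants, 0.3 between fluids and 0.3 residual, s = √(0.64 + 0.09 + 0.09) = 0.906. All limits are 100 (2.0 log10) unless stated.

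- *Start 3.5, fall 1.0, offset 1.0.* Day 1: 3.470 - 2.375 = 1.095. Month 6: 2.375 - 1.455 = 0.920. Change per month: (0.920 - 1.095)/6 = -0.029.
- *The same with fall 1.5.* Month 6: 1.861 - 1.196 = 0.665. Change per month: (0.665 - 1.095)/6 = -0.072.
- *Start 4.2, fall 1.0, offset 0.5.* Day 1: 4.195 - 3.680 = 0.515. Month 6: 3.147 - 2.594 = 0.553. Change per month: +0.006, so the sign can reverse.
- *Zero offset, equal limits.* The two means are identical at each visit and the difference is 0.
- *Zero offset, limits 100 and 316, start 3.5, fall 1.0.* Day 1: 3.470 - 3.360 = 0.110. Month 6: 2.375 - 2.111 = 0.264. A difference and a trend appear where neither exists.

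**5. Rejection rates, same SDs.** 400 simulated trials per setting, whole blood start 3.5, mean of per-infant linear slopes tested by t test. Monte Carlo error near 5% is √(0.05 × 0.95/400) = 1.1 points.

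| Setting | Offset 0.3 | Offset 0.5 | Offset 1.0 |
|---|---|---|---|
| Limit 100, fall 1.0: slope per month | -0.003 | -0.008 | -0.032 |
| Limit 100, fall 1.0: rejected | 5% | 16% | 93% |
| Limit 100, fall 1.5: slope per month | -0.015 | -0.029 | -0.077 |
| Limit 100, fall 1.5: rejected | 44% | 91% | 100% |
| Limit 10, fall 1.5: rejected | 44% | 91% | 100% |

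The limit-10 row shows that the problem is not only a poorly chosen constant. Zero offset with equal limits, or no fall in load, gave 3-8%. Zero offset with limits of 100 and 316 gave slopes of ±0.020 and 54-56%. The same data uncensored gave 2-8%.

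**6. Wider range.** With a 1.5 log fall, equal limits of 10 to 300 and offsets of 0.5 to 1.0, rejection was about 37-100% at a 3.5 start, 3-90% at 4.0 and 6-40% at 4.5, against about 3-8% uncensored. The false slope ran from about -0.11 to +0.02 log10 per month, that is, -0.66 to +0.12 log10 over six months.

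**7. Does censoring help?** A marginal left-censored normal model with a fluid-by-time slope (limit 100, five settings, 200 trials each) gave mean slopes of -0.002 to +0.001 per month and 6-9% rejection (Monte Carlo error about 1.5 points). At start 3.5 and fall 1.0, rejection went from 93% to 8% with offset 1.0, and from 16% to 6% with offset 0.5.

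**The case against.** *A reader might infer that substitution makes the plan wrongly declare that the fluids differ.* With equal limits the documents do not support that. The plan's stated conclusion is that average loads differ, and wherever a trend appeared with equal limits a true offset was present, so that conclusion would be correct. Only the change over time is false. A difference where none exists requires unequal limits. The documents name one central laboratory and do not say whether the limits are equal. This objection stands and limits the point to the trend.

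*The simulations are not the plan's analysis.* The plan chooses among linear, quadratic and cubic time, selects a covariance structure by AIC, and tests the slope only if a line fits. The rates above come from straight lines per infant with complete data. Section 8.2 ranks virology last when blood is short, and 176 is the number evaluable for hearing, not a count of viral load series. This also stands: the rates are not the plan's error rates. It does not remove the distortion, which is in the recorded values before any covariance is chosen. A curved artefact would lead to the plan's other branch, which also reads the result as a difference.

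*The objective is exploratory.* True, and it limits the priority of the point rather than its validity.

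**Conclusion.** The point holds in a limited form. Substituting 10 in both fluids can create a false time trend in the paired difference when the undetectable share changes over time and either a constant offset exists or the limits differ. The simulations give both fluids the same spread; under that assumption, zero offset with equal limits gives no inflation.

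The size cannot be fixed from the documents. Over the assumed settings it runs from no visible inflation to near-certain rejection of a true zero slope. It is worst at low starting loads and large offsets, and it varies with the shape of the fall.

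A reader might also infer that the hearing analysis is distorted, because section 11.4.4 relates viral load to hearing. The section does not define the viral load predictor, and no calculation was made, so no such claim is made here. The primary hearing estimate does not use viral load and is unaffected. This is a worthwhile, low-cost improvement to an exploratory analysis.

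**What to change.** In section 11.4.4:

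- State the detection limit of each fluid's assay.
- Report the proportion undetectable by visit and fluid.
- Fit log10 viral load with a left-censored (Tobit-type) repeated-measures model, with each fluid's limit as its censoring point.
- Compare the fluids through a fluid-by-time term in one joint censored model, not by subtracting substituted values.
- Keep substitution of 10 as a sensitivity analysis.

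No extra infants, visits or samples are needed. The cost is more programming and a change of wording which, because the rule is in the protocol, may require an amendment. The downside is reliance on normality, which is weakest where most values are undetectable. The check above used a marginal censored model, so the joint repeated-measures version should be tested on simulated data before it is adopted.
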